**Protocol Revision History**

Initial Approval Version	03/14/2017
Amendment #1 Version	05/24/2017
Amendment #2 Version	11/16/2017
Amendment #3 Version	01/04/2018
Amendment #4 Version	05/17/2018
Amendment #5 Version	08/31/2018
Amendment #6 Version	02/21/2019
Amendment #7 Version	05/28/2020

**An open label, multicenter, phase II trial testing single agent decitabine in *TP53* mutated relapsed/refractory acute myeloid leukemia**

## Glossary of Abbreviations

AE	Adverse event
ALT (SGPT)	Alanine transaminase (serum glutamate pyruvic transaminase)
AML	Acute myeloid leukemia
t-AML	Therapy-related Acute myeloid leukemia
s-AML	Secondary Acute myeloid leukemia
ANC	Absolute neutrophil count
AST (SGOT)	Aspartate transaminase (serum glutamic oxaloacetic transaminase)
BMT	Bone marrow transplant
BM	Bone marrow
CBC	Complete blood count
CNS	Central nervous system
CR	Complete response
CRc	Cytogenetic complete remission
CRi	Complete remission incomplete hematologic recovery
CT	Computed tomography
CTCAE	Common Terminology Criteria for Adverse Events
DNA	deoxyribonucleic acid
DSM	Data and Safety Monitoring
DSMC	Data Safety Monitoring Committee
ECG (or EKG)	Electrocardiogram
EDTA	ethylenediaminetetraacetic acid
FDA	Food and Drug Administration
FISH	fluorescent in situ hybridization
GCP	Good Clinical Practice
HB	Hemoglobin
HHS	Department of Health and Human Services
HI	Hematologic improvement
HIV	Human Immunodeficiency Virus
HRPO	Human Research Protection Office (IRB)
IRB	Institutional Review Board
ITT	Intention to Treat
MDS	Myelodysplastic syndrome
mLFS	Morphologic leukemia free state
MM	Multiple myeloma
MPN	Myeloproliferative neoplasm
MRI	Magnetic resonance imaging
NCI	National Cancer Institute
NIH	National Institutes of Health
OHRP	Office of Human Research Protections
ORR	Overall response rate

OS	Overall survival
PBMC	Peripheral blood mononuclear cell
PB	Peripheral blood
PD	Progressive disease
PI	Principal investigator
PR	Partial remission
QASMC	Quality Assurance and Safety Monitoring Committee
RFS	Relapse free survival
SAE	Serious adverse event
SAP	Statistical Analysis Plan
SCC	Siteman Cancer Center
SCT	Stem cell transplant
SD	Stable disease
TSH	Thyroid stimulating hormone
TTLR	Time to leukemia relapse
UPN	Unique patient number
WBC	White blood cell count

**SCHEMA**

A bone marrow biopsy may be performed at any time after Cycle 2 if there is clinical concern for progression.

Patients with progressive disease after 2 cycles of decitabine (10 days each) may be removed from study.

After Cycle 2, decitabine dose will be reduced FOR ALL PATIENTS from 20 mg/m^2/day x 10 days to 20 mg/m^2/day x 5 days. After Cycle 1, patients with blast counts <5% may reduce decitabine dose from 20 mg/m^2/day x 10 days to 20 mg/m^2/day x 5 days. Each cycle is 28 days.

Notes for transplant eligible patients

Anytime after 3 cycles, transplant eligible patients in **CR, CRc, CRi, or mLFS\*** should **proceed to stem cell transplant** according to institutional protocols.

After 3 cycles, transplant eligible patients in **PR\*** may be removed from study and proceed to salvage according to institutional protocols.

Notes for transplant ineligible patients

Transplant ineligible patients **will continue on study with decitabine (x 5 days)** until relapse or progression, with the exception of patients with **SD\*** after 4 cycles who may continue on therapy or be removed from study per treating physician preference.

Antimicrobial prophylaxis during therapy is strongly recommended due to anticipated neutropenia. Common agents include acyclovir, ciprofloxacin, and fluconazole. Alternative agents may be used at the discretion of the treating physician.

Correlative samples:

BM and PB should be collected on Cycle 1 Day 0 (C1D0), Cycle 1 Day 10 (C1D10)\*\*, Cycle 1 Day 28 (C1D28), Cycle 2 Day 28 (C2D28)\*\*\* and Cycle 3 Day 28 (C3D28). A skin biopsy should be done on C1D0 (buccal swab may be substituted for skin if patient declines skin biopsy). A buccal swab should be done on C2D28. BM and PB should be collected at the time of progression (if possible).

\*For definition of responses see Section 12

\*\* Bone marrow aspirate and biopsies on cycle 1 day 10 will only be performed in patients enrolled at Washington University.

\*\*\* At the discretion of the treating physician.

## 1.0 BACKGROUND AND RATIONALE

### 1.1 Introduction

Acute myeloid leukemia (AML) is an aggressive, relapsing blood cancer characterized by ineffective hematopoiesis and malignant expansion of clonal myeloid cells and a broad variety of genetically distinct sub-types.

Through next generation sequencing techniques, we have identified patterns of somatic mutations commonly associated with AML and found that these mutations organize into founding clones and subclones.

Treatment options for AML remain limited, and personalized strategies are needed. The 5-year overall survival among patients with AML age 25-64 is 40%. Both clinical and genomic prognostic markers have been identified, including age, performance status, type of AML (de novo, AML with antecedent hematopoietic malignancy, or therapy-related AML), response to induction treatment and, most importantly, genetics.

Cytogenetic abnormalities have been one of the most important prognostic markers for risk stratification. Specifically, patients with complex karyotype or monosomy karyotype are associated with adverse risk, and often carry mutations in *TP53*. In this population, standard cytotoxic chemotherapy and allogeneic stem cell transplantation result in 5-year survival of less than 10% and a median survival of only few months, and many patients even fail to achieve complete remission after induction chemotherapy.

We recently observed that AML and myelodysplastic syndrome (MDS) patients with *TP53* mutations have high response rates to decitabine. In this study we will determine whether decitabine leads to an increase in overall survival in patients with *TP53* mutated AML, who have detectable disease after initial induction chemotherapy. These patients represent the group with the poorest prognosis, and alternative therapy is desperately needed.

[figure not shown]
### 1.2 Study Rationale

Among patients with complex or monosomy karyotypes, nearly 60% carry *TP53* mutations; whereas nearly all patients with *TP53* mutations have complex or monosomy karyotypes, and these karyotypes almost always involve deletion of chromosome 5q, chromosome 7, chromosome 12, or chromosome 17p. Patients with *TP53* mutations tend to be older (median age 61 vs 54 years), have worse response to conventional chemotherapy (complete remission rate: 28% vs 50%), shorter event free survival (3-year EFS: 1% vs 13%), and overall survival (3-year OS: 3% vs 28%).

We correlated response to decitabine with mutation status in 99 patients with AML or MDS. We observed response (complete remission (CR), complete remission with incomplete blood count recovery (CRi), or marrow complete remission (mCR) in 21/21 patients with *TP53* mutations. ( $p < 0.0001$ ). No other gene mutation was associated with

response in the 99 patients sequenced (Figure 1A).

Consistent with this, we observed mutation clearance in all 16 cases with TP53 mutations evaluated at serial time points, and that TP53 mutations were cleared more quickly and consistently than other variants (Figure 2).

Decitabine alone does not lead to a cure in the majority of responding patients. Mutation clearance is nearly always incomplete, and we could detect low levels of mutations (0.2 - 5%) in 20 of 20 patients analyzed during remission with enhanced exome sequencing. Furthermore, in all 9 patients analyzed at relapse, the relapse occurred via subclonal evolution (expansion of a subclone that carries the founding clone mutations and additional mutations, suggesting that the founding clone mutations persisted during morphologic remission).

Several clinical variables correlated with survival in this cohort: age, performance status (2 vs 0-1), and whether the patient underwent stem cell transplantation (Figure 3A). Thus, additional consolidation (e.g. hematopoietic cell transplantation) appears necessary to

achieve prolonged remissions. Importantly, in this cohort of patients who undergo decitabine induction, the presence of *TP53* mutations no longer adversely affected survival following transplantation.

These data suggest that decitabine may have unique efficacy in patients with *TP53* mutations. In this study, we seek to determine whether decitabine therapy can improve outcomes, specifically overall survival, of this selected subset of AML patients with the poorest prognosis based on refractoriness to induction treatment and high-risk genetic mutations.

[figure not shown]

Figure 2. Consistent clearance of *TP53* mutations. A. The variant allele frequency of *TP53* mutations was consistently reduced during decitabine treatment. Twenty-one *TP53* mutations were evaluated at multiple time points in 16 patients, (e.g. cycle 2 day 28, C2D28). Variant allele frequency indicates the proportion of variant reads vs. the total number of reads at that nucleotide, and is proportional to the tumor burden. B and C. Mutation clearance of *SRSF2* and *DNMT3A* mutations. D. Summary of rate of mutation clearance. Note that during decitabine therapy, *TP53* mutations were consistently, and rapidly, cleared when compared with mutations in other genes. P value calculated with ANOVA using Tukey’s post-test correction.

[figure not shown]

Figure 3. Overall survival subgroup analysis. A. Overall survival was increased in patients treated with 10 day decitabine who underwent stem cell transplantation vs. those who did not. B. Among patients who underwent stem cell transplantation, survival was not impacted by the presence or absence of *TP53* mutations. P value calculated as Log-rank.

### 1.3 Investigational Agent

Decitabine (5-aza-2'-deoxycytidine) is a DNA hypomethylating agent. Decitabine is an antimetabolite that can replace cytosine in DNA but, unlike cytosine, it cannot be methylated. The exact mechanism of decitabine activity has not been determined and may involve multiple pathways. Decitabine is thought primarily to act by altering DNA methylation, a major mechanism for gene expression. Methylation of cytosine in the CpG dinucleotide by DNA methyltransferase leads to transcriptional silencing of genes during normal development and has emerged as a significant mechanism for the loss of tumor suppressor gene expression in human cancer, including AML. Decitabine regulates DNA methylation (specifically targets the methyltransferase, *DNMT1*), effectively demethylating and reactivating different tumor suppressor genes. Other possible mechanisms for decitabine activity include cytotoxicity due to incorporation into DNA during S phase and formation of covalent adducts with DNA methyltransferase. The irreversible inhibition and degradation of DNA methyltransferase 1 results in methylation-independent induction of gene expression and it is associated with differentiation. In addition to its differentiation inducing activity at low doses, decitabine has a direct cytotoxic effect at higher doses (1-2  $\mu\text{M}$ ).

Decitabine has been investigated in hematologic malignancies using a range of doses and schedules. Two dosing regimens are approved in the US compendium. A dose of 15 mg/m^2 every 8 hours for 3 days, based on a Phase III study in adults with MDS that demonstrated improved outcomes in the treatment arm compared to the supportive care arm^14. And the dose of 20 mg/m^2 daily for 5 days in 28-day cycles is also approved.

In general, decitabine is well tolerated. Unlike conventional cytotoxic chemotherapy, decitabine can be administered in the outpatient setting. Cytopenias commonly result from AML/MDS inhibition of normal hematopoiesis, and often do not resolve until a complete response is achieved. Thus, neutropenic sepsis and thrombocytopenic bleeding remain significant problems regardless of therapy, especially during the first 4-8 weeks. In our experience treating elderly AML patients, neutropenia occurred in 24%, sepsis in 9%, and bacteremia in 7%. Similar results have been observed in MDS patients. As a result, death is not uncommon in the first 8 weeks of therapy, occurring in 15-17% of patients, and most commonly resulting from infection and cytopenias related to disease and therapy. While unsettling, these numbers are better than many historical patients treated with cytotoxic chemotherapy, and suggest a need for continued improvements in therapy.

#### A. Pharmacokinetics and Metabolism of Decitabine

In human subjects, after IV administration, decitabine displayed a distribution phase with a half-life of 7 minutes and a terminal phase elimination half-life of 10-35 minutes as measured by bioassay. The short plasma half-life is due to rapid inactivation of decitabine by deamination by liver cytidine deaminase. Total body clearance (Clp) in humans was high with a mean value of 126 mL/min/kg.

Among five adult patients with advanced solid tumors administered seven courses of 100 mg/m^2 of decitabine by 1-hour infusions, maximum plasma concentration ranged from 1 to 4 μM. Disappearance from plasma was biphasic with a rapid initial decline to less than 0.1 μM during the first hour post infusion and a slower decline over the next two hours to 6 nM, the level of detectability. Plasma half-life (mean±SE) was estimated to be approximately 7±1 minutes in the initial phase (t1/2α) and 35±5 minutes in the second phase (t1/2β). The area under the plasma concentration-time curve was 408±88 ng.hour/mL for these patients, with a peak plasma concentration of 2.01±0.44 μM (0.44±0.1 μg/mL), while mean volume of distribution (Vdss) and CLp was 4.59±1.42 L/kg and 126±21 mL/min/kg, respectively. The time course of DAC concentrations was similar in 1 of 2 patients administered 75 mg/m^2, while DAC was usually undetectable in the plasma of patients administered 25 to 60 mg/m^2.

Using a longer infusion time (up to 40 hours), Rivard *et al.* reported a plasma concentration of 0.1 to 0.4 μg/mL. With infusion times of 40-60 hours, at an infusion rate of 1 mg/kg/h, plasma concentrations of 0.43-0.76 μg/mL were achieved. The steady-state plasma concentration at an infusion rate of 1 mg/kg/h was estimated to be 0.2-0.5 μg/mL. The half-life after discontinuing the infusion was 12-20 min.

Urinary excretion of unchanged decitabine was low, ranging from less than 0.01% to 0.9% of the total dose, and there was no relationship between excretion and dose or plasma drug levels. High clearance values and a total urinary excretion of <1% of the administered dose suggest that decitabine is eliminated rapidly and largely by metabolic processes, including extrahepatic metabolism^22.

[figure not shown]
The steady state plasma concentrations (Css) ranged from 0.31 to 0.39 μg/mL (1.27 to 1.60 μM) during the infusion of 100 mg/m^2 decitabine over a 6-hour period. The range of concentrations during a 600 mg/m^2 infusion over an 8-hour period was 0.41-16 μg/mL (1.68 to 4.76 μM). These plasma concentrations are in the same range as the in vitro concentrations that activated the expression of tumor suppressor gene p16 in three human non-small-cell lung cancer (NSCLC) cell lines.

Steady state decitabine levels of 0.1 to 0.2 μM were achieved in solid tumor patients dosed with 30 mg/m^2/day and 40 mg/m^2/day by continuous intravenous infusion over 72 hours.

Summary of published steady state serum levels are below and are in proportion to infusion rate (R^2 = 0.98, p < 0.0001).

Rate	Serum Concentration	
	ng/ml	nM
5	55	241
7.5	80	351
15	180	789
21	182.4	800
22.5	350	1535
42	456	2000
84	1140	5000

In our experience treating primary patient blasts *in vitro*, concentrations of 100 – 500 nM are required to maximize methylcytosine reduction without causing cellular toxicity. Because decitabine incorporation into DNA is S-phase dependent, exposure of cells during cell division is necessary for efficacy.

## B. Experience with extended dosing schedules

Decitabine does not act quickly and the median time to response is 3 months. Several doses have been tested and reported in the literature with doses ranging from 5 mg/m^2/day for 5-10 days to doses of 135 mg/m^2/day for 3 days.

From our experience and from another report there is data to support that lower doses over longer periods of time results in significant improvement in response rate and have lower toxicity.

The mechanism underlying this observation is unclear, however there are some reports that suggest that at lower doses (e.g. 20 mg/m^2), decitabine might promote cell differentiation through effective methylcytosine reduction and gene expression derepression, as opposed to induction of apoptosis via DNA damage that is seen at

higher doses (e.g. 100 mg/m^2) and it is more typical of conventional chemotherapeutic agents.

Lower dose schedule (20 mg/m^2/day) on days 1-5 became the standard strategy based on a series of studies. However, subsequent studies using longer dose schedules (days 1-10) found that this led to improved response rates.

Therefore, we will use a dose of 20 mg/m^2/day as a 1-hour intravenous infusion on consecutive Days 1-10 in 28-day cycles, dose reductions for subsequent cycles will be allowed as described in Sections 5.1 and 6.3.

## 2.0 OBJECTIVES

### 2.1 Primary Endpoint

To determine the 1-year OS in patients with *TP53* mutations treated with at least one dose of decitabine compared to historic controls (OS = 25%).

### 2.2 Secondary Endpoints

1. To determine the proportion of responding *TP53* mutated patients (CR, CRi) compared to historical controls (10%-15%)
2. To determine the time to stem cell transplant among subjects who are suitable candidates for transplant and have an identified donor.
3. To correlate response and survival with clinical parameters:
  - morphologically evident disease (>5% blasts by cytomorphology) versus molecularly detected disease at the time of enrollment (disease detected with flow cytometry, cytogenetic, or mutational analysis if ≤ 5% blasts by cytomorphology);
  - *de novo AML versus secondary AML versus treatment-related AML*,
  - presence *versus* absence of cytogenetic abnormalities in addition to *TP53* mutations.
4. To determine the median time to leukemia relapse (TTLR) in non-transplant patients treated with decitabine compared to historical control (6-8 months).
5. To determine the 2-year event free survival after transplant in patients treated with decitabine compared to historical control (18-22%).
6. To determine the median and average number of hospital days during Cycles 1 and 2.

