## 3.0 PATIENT SELECTION

### 3.1 Inclusion Criteria

1. *TP53* mutant AML. The presence of a *TP53* mutation should be determined by Genoptix (or institutional preferred equivalent assay). Detection of a *TP53* mutation at the time of initial diagnosis is sufficient for enrollment at the time of relapsed/refractory disease. Detection of a *TP53* mutation in either the peripheral blood or bone marrow is adequate for enrollment. (Refer to Appendix B for definition of *TP53* mutant AML.) Alternatively, patients who have not had *TP53* mutation analysis performed, but who have > 20% *TP53* positive cells by immunohistochemistry detected on a bone marrow aspirate may also be enrolled, provided that mutation analysis is requested at the time of enrollment.
2. Relapsed/refractory AML following 7+3 (or similar cytarabine containing induction chemotherapy for AML) disease detected by one of the following methods:
  - Bone marrow blasts > 5%, or
  - Hematologics flow cytometry assay (threshold > 0.5%) (alternative equivalent assay may be substituted), or
  - Persistent cytogenetic abnormality (e.g. del5, del17p, etc) by FISH or conventional karyotyping, or
  - Persistent *TP53* mutation (at least 5 variant reads with at least 50x coverage) determined by Genoptix (or institutional preferred equivalent assay).

Patients with > 10% blasts on a Day +14 bone marrow biopsy following 7+3 may either be enrolled or may be treated with a course of standard re-induction (e.g. 5+2 or similar) and then re-evaluated for response. Eligible patients will meet any of the above criteria on a subsequent biopsy.

3. Bone marrow and organ function as defined below:
  - Peripheral white blood cell count < 50,000/mcl (patients may receive hydroxyurea as necessary for cytoreduction),
  - Total bilirubin < 1.5 x upper limit of normal,
  - AST and ALT < 2.5 x upper limit of normal,
  - Serum creatinine < 2.0 x upper limit of normal, and,
4. At least 18 years of age.
5. Women of childbearing potential and men must agree to use adequate contraception (hormonal or barrier method of birth control, abstinence) prior to study entry and for the duration of study participation. Should a woman become pregnant or suspect she is pregnant while participating in this study, she must inform her treating physician immediately
6. Ability to understand and willingness to sign an IRB approved written informed consent document (or that of legally authorized representative, if applicable)

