## 12.0 MEASUREMENT OF EFFECT

### 12.1 Response assessment

Bone marrow biopsy will be obtained on Cycle 1 Day 28 ± 4, Cycle 2 Day 28 ± 4, and Cycle 3 Day 28 ± 4. The cycle 2 Day 28 collection may be performed at the discretion of the treating physician.

All patients will be assessed for response according to the 2017 ELN AML Recommendations:

*Complete remission (CR)* – Defined as bone marrow blasts <5%; absence of circulating blasts and blasts with Auer rods; absence of extramedullary disease; absolute neutrophil count  $\geq 1.0 \times 10^9/L$  (1,000/ $\mu$ L); platelet count  $\geq 100 \times 10^9/L$  (100,000/ $\mu$ L).

*Complete remission with incomplete hematologic recovery (CRi)*: All CR criteria except for residual neutropenia -  $< 1.0 \times 10^9/L$  (1,000/ $\mu$ L) or thrombocytopenia -  $< 100 \times 10^9/L$  (100,000/ $\mu$ L)

*Cytogenetic complete remission (CRc)* – Defined as morphologic complete remission plus a reversion to a normal karyotype. For this study, reversion of a normal karyotype is defined as no clonal abnormalities detected in a minimum of 20 mitotic cells.

*Morphologic leukemia free state (mLFS)*: Defined as bone marrow blasts <5%; absence of blasts with Auer rods; absence of extramedullary disease; no hematologic recovery required. Marrow should not merely be “aplastic”; at least 200 cells should be enumerated or cellularity should be at least 10%

*Partial remission (PR)* – Defined as all hematologic criteria of CR; decrease of bone marrow blast percentage to 5% to 25%; and decrease of pretreatment bone marrow blast percentage by at least 50%.

*Stable Disease (SD)* – Defined as not meeting the definitions of CR, CRi, PR, PD, or recurrence/morphologic relapse.

*Progressive disease (PD)* – Defined as a clear increase in bone marrow blast count, typically a greater than 50% increase compared with baseline, or new extramedullary disease. Patients with a > 50% increase in peripheral blast count with an increase of the total peripheral white blood cell count to > 10,000/ $\mu$ l should undergo evaluation by bone marrow biopsy to assess for progressive disease. Patients enrolled with a bone marrow blast count < 20% will have > 20% blasts and a > 50% increase compared with baseline.

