### **15.2 Analysis Populations**

Intent-to-Treat - Defined as all patients who receive at least one dose of decitabine.

Efficacy-Evaluable - Defined as all patients who receive at least one cycle of treatment.

Safety - Defined as all patients with at least one dose of decitabine.

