## **E. Secondary Clinical Endpoints Analyses**

The principal measurement of toxicity will be a measure of the total number hospitalized days during the first 60 days of therapy.

**CRc rate** will be analyzed based on the ITT population. The remission rate and its 2-sided 90% confidence interval (CI) will be summarized.

**Event-free survival:** EFS will be analyzed using Kaplan-Meier methodology and Kaplan-Meier plots will be provided using the ITT analysis set. The median EFS and its 2-sided 90% CI using the complementary log-log transformation method (Collett 1994) will be calculated.

**Leukemia-free survival:** LFS will be analyzed using Kaplan-Meier methodology

and Kaplan-Meier plots will be provided using the ITT analysis set. The median LFS and its 2-sided 90% CI using the complementary log-log transformation method (Collett 1994) will be calculated.

**Time to leukemia relapse:** TTCR will be summarized using descriptive statistics.

The time to stem cell transplant, the proportion of patients who are able to undergo transplantation, and the average number of hospital days during cycles 1 and 2, will also be documented. The association between response and clinical characteristics (morphologically evident disease -i.e., >5% blasts by cytomorphology- versus molecularly detected disease at the time of enrollment -i.e., disease detected with flow cytometry, cytogenetic, or mutational analysis with  $\leq 5\%$  blasts by cytomorphology-, *de novo AML versus secondary AML versus treatment-related AML*, presence *versus* absence of cytogenetic abnormalities in addition to *TP53* mutations, etc.) will be described using contingency tables and compared by Chi-square test or Fisher's exact test as appropriate. The association between survival (OS, EFS, LFS) and clinical characteristics will be described using Kaplan-Meier methods and compared by log-rank test.

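### Patients can enter already meeting CR or CRi, and the plan does not take them out of the CR+CRi rate it compares with a historical 10-15%

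*Combined protocol and SAP*

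**What the plan says.** Section 2.2 item 1 sets a secondary endpoint: the proportion of responding TP53 "mutated patients (CR, CRi) compared to historical controls (10%-15" percent).

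Inclusion criterion 2 in Section 3.1 accepts disease shown by any one of four methods. One is marrow blasts above 5%. The other three carry no blast minimum: flow cytometry above 0.5%, "Persistent cytogenetic abnormality (e.g. del5, del17p, etc) by FISH or conventional karyotyping", or a persistent TP53 mutation. Low-blast entry is expected, because Section 2.2 item 3 plans to compare "morphologically evident disease (>5% blasts by cytomorphology) versus molecularly detected disease at the time of enrollment", the second group having 5% blasts or fewer.

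Section 12.1 describes CR as "Defined as bone marrow blasts <5%; absence of circulating blasts and blasts with Auer rods; absence of extramedullary disease", plus neutrophil and platelet thresholds; CRi relaxes the count recovery. PR, by contrast, needs a "decrease of pretreatment bone marrow blast percentage by at least 50" percent, and PD has a special rule for patients enrolled with fewer than 20% blasts. CR and CRi have no baseline condition of either kind.

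Section 15.2 gives the ITT set as "Defined as all patients who receive at least one dose of decitabine"; the efficacy-evaluable set asks only for one cycle. Section 15.4.E specifies an analysis for one remission rate, CRc, which "will be analyzed based on the ITT population. The remission rate and its 2-sided 90% confidence interval (CI) will be summarized". It gives no separate analysis for CR+CRi.

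**The concern.** A patient enrolled on flow, cytogenetics or TP53 persistence, with fewer than 5% marrow blasts and no circulating blasts, Auer rods or extramedullary disease, meets CR or CRi before treatment starts. Scored by Section 12.1 as written, that patient is a responder if nothing changes. The CR+CRi proportion could then exceed 10-15% because of who was enrolled and not because of decitabine.

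The same mixing reaches the comparisons in Section 15.4.F between patients who reach CR/CRi and those who do not, the table of response by disease type in Section 15.4.E, and the treatment-failure definition in Section 12.1.A. The primary endpoint, its power and the futility rule rest on overall survival and are untouched.

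**Working it through.** The plan states no test, power or sample size for CR+CRi, so there is no figure of its own to reproduce.

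**Step 1: entry routes against the response definition.**

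| Entry route (3.1) | Blast minimum | Can CR/CRi hold at entry? |
|---|---|---|
| Marrow blasts above 5% | above 5% | No, CR/CRi need below 5% |
| Flow above 0.5% | none | Yes |
| Persistent cytogenetic abnormality | none | Yes |
| Persistent TP53 mutation | none | Yes |

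Not every low-blast patient qualifies: exactly 5% blasts, circulating blasts, Auer rods or extramedullary disease each prevent it.

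**Step 2: inputs for size.** N = 60 (15.4.G); p = 10% or 15% for the other patients, i.e. no drug effect (2.2). Two quantities are not in the documents and are assumed:
- m, the number in CR/CRi at entry: 3, 6 or 12 (5%, 10%, 20% of 60);
- q, the share of them still scored CR/CRi on study: 100%, 84% or 50%. The 84% removes only early deaths, at the middle of the 15-17% quoted in Section 1.3.

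**Step 3: formula.** Expected rate = [m q + (60 - m) p] / 60, so bias = (m/60)(q - p). It is upward only if q > p.

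Example: m = 6, q = 1, p = 0.10 gives (6 + 54 x 0.10)/60 = 11.4/60 = 19.0%.

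| p | q | m = 3 | m = 6 | m = 12 |
|---|---|---|---|---|
| 10% | 100% | 14.5% | 19.0% | 28.0% |
| 10% | 84% | 13.7% | 17.4% | 24.8% |
| 10% | 50% | 12.0% | 14.0% | 18.0% |
| 15% | 100% | 19.25% | 23.5% | 32.0% |
| 15% | 84% | 18.45% | 21.9% | 28.8% |
| 15% | 50% | 16.75% | 18.5% | 22.0% |

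**Step 4: how few are enough.** With p = 10%, the expected rate passes 15% when m > 3/(q - 0.10). That is 4, 5 or 8 patients at q = 100%, 84% or 50% (16.0%, 16.2%, 15.3%).

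**Step 5: when the drug works.** At p = 50% the bias for m = 3, 6, 12 is +2.5, +5 and +10 points at q = 100%, and zero at q = 50%. At p = 70% and q = 50% it is -1, -2 and -4 points.

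**Step 6: worked example.** Take m = 6, all retained, and 8 responders among the other 54. Counting everyone gives 14/60 = 23.3% (exact 90% CI 14.7-34.0%). Setting the six aside gives 8/54 = 14.8% (7.6-25.1%). The first interval's lower limit is close to the top of the historical range; the second interval contains the whole range.

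**The case against.** The strongest reply is that the counting rule is inferred. Section 2.2 speaks of *responding* patients, and other sections of patients who *achieve* remission, which can be read as a state reached on treatment. The plan also names no analysis set for CR+CRi; the ITT sentence in 15.4.E is about CRc. Both observations are accurate, but neither term is defined as a change from baseline, Section 12.1 applies its criteria to all patients, and both efficacy sets in 15.2 admit these patients.

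Second, safeguards exist:
- CRc is "Defined as morphologic complete remission plus a reversion to a normal karyotype", and Section 1.2 says nearly all TP53-mutated patients have complex or monosomy karyotypes, so CRc is largely protected. But CRc is not the endpoint in 2.2 item 1, and a patient enrolled by flow, FISH or TP53 with a normal 20-cell karyotype is not covered.
- The response table already splits at 5% blasts, and its upper row cannot contain anyone in CR/CRi at entry. But it is an association analysis, and the historical comparison is not tied to that row.
- Mutation clearance below 0.1% (2.3) is a separate endpoint.

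Third, the size is unanchored. This stands: m and q are unknown, and the 21/21 responses in Section 1.2 (AML and MDS mixed, marrow CR counted) show that a high p is possible, where the bias shrinks or reverses. The historical denominator is not described either; if that series included similar patients, the bias would be smaller. And no decision rule uses this rate, which limits the severity but not the need for a readable comparison.

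**Conclusion.** The concern holds. As written, the plan lets patients who already meet CR/CRi at entry count as responders in the proportion set against 10-15%. With no drug effect, 3 to 12 such patients among 60 move the expected rate to 12-28% if the others respond at 10%, and to about 17-32% if they respond at 15%, for q between 50% and 100%. At 10%, three patients never take the rate past 15%, and six do not at q = 50%.

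The gap in definitions is certain from the text. Its size rests on the assumed m and q, and on a historical denominator that cannot be checked. The low-p case is the one that matters, because there entry status could be mistaken for activity. This should be fixed, but it concerns a secondary endpoint only.

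**What to change.** - In 2.2 item 1 and 15.4.E, estimate CR+CRi with its 90% CI, and compare it with 10-15%, in dosed patients who do not meet all CR/CRi criteria at baseline. Judge this from the last pre-dose marrow, the CBC with differential, and extramedullary status on the baseline exam.
- Show the stratum above 5% blasts as a sensitivity analysis.
- Report patients in CR/CRi at entry separately, by clearance of the flow, cytogenetic or TP53 marker that qualified them. The below-0.1% clearance endpoint covers part of this.
- In the table of response by disease type, exclude them or give them their own row. Apply the same rule to the CR/CRi comparisons in 15.4.F, and state in 12.1.A how they count for treatment failure.
- State which patients form the denominator of the historical 10-15%.

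The cost is wording plus one data field. Baseline marrow (5.1.A), CBC and exam (5.1.B) and a baseline Disease Assessment Form (11.0) are already required. A patient whose extramedullary disease the exam misses would be wrongly set aside. Precision falls slightly: the exact 90% CI is 16.7 points wide at 9/60 (8.1-24.7%), 17.6 at 8/54 (7.6-25.1%) and 18.6 at 7/48 (7.1-25.7%), with widths taken from unrounded limits.
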